### Standard of care procedures

Subject is placed under general anesthesia and positioned face down. The neurophysiology team places subdermal needles for MEP, SSEP and EMG measurements and connects the wires to the **IOMAX intraoperative neuromonitoring system** (owned and paid for by MUSC). Skin incision is made. The SCS paddle is placed into initial position.

The neurophysiology team then performs MEP and SSEP measurements. The surgeon makes small adjustments to the position of the paddle based on this information.

Once the SCS paddle is in its final position, the SCS paddle terminals are disconnected from the LR10 machine and reconnected to a **Boston Scientific external stimulator** (owned and paid for by Boston Scientific – leaves the OR with Boston Scientific representative). The stimulator tests the impedance of each contact.

### Research procedures

Once the SCS paddle is in initial position, the research team connects the SCS paddle terminals to the **LR10 machine** (owned and paid for by the [name] lab, takes less than 1 minute).

The research team saves data from the SCS paddle as the MEP and SSEP measurements are performed (takes 0 minutes).

Once the impedances are confirmed, the external stimulator is used to test each contact on the paddle and compare low- and high-frequency stimulation patterns as prescribed by the study protocol (takes approximately 15 minutes).

### **Step 2: Proprioception testing before, during and after SCS stimulation**

All of the following are for research purposes and not considered standard of care for SCS surgery. Following an approximately 30-day recovery period from surgical placement of the paddle and IPG, subjects will undergo

Date: 8/1/19

Version: 01

stimulation configuration mapping (SCM) in the Locomotor Rehabilitation Laboratory at the College of Health Professions Building C at MUSC in order to determine electrode and parameter configurations that elicit activation of lower extremity musculature. For this testing, we will place surface EMG pads on subjects' skin overlying muscles of interest. Using the Boston Scientific external stimulator interface, we will wirelessly activate the implanted spinal paddle and compare muscle activation using LFTS and HFBS patterns by systematically testing each individual contact. Subjects will comfortably lie supine on a large, low-rise rehabilitation mat common to any physical rehabilitation clinic during SCM.

Next, we will investigate the perceived change in knee joint angle and direction of movement reported by the subject in a Threshold to Detect Passive Movement (TTDPM) task. The TTDPM protocol will begin with the subject sitting in the Biodex testing seat, with the non-tested leg hanging freely and the tested leg strapped to the rotating arm of the dynamometer at the lower shank. The subject will be blinded as to the mode and intensity of stimulation: HFBS, LFTS, or no stimulation. Furthermore, in order to shield the subject from witnessing initiation, direction and approximate distance traveled of the shank, the subject will be asked to wear a blindfold and headphones playing a soft background noise (Figure 3). The TTDPM will consist of at least 10 trials for each stimulation condition. The subject has control of a switch that immediately halts movement of the rotating arm, which is to be activated once the subject perceives movement **OR** if the subject begins to feel any pain or discomfort throughout the task. Our research team anticipates data collection to last approximately 3 hours per subject for this step (1 hour for supine SCM, 1 hour for TTDPM and 1 hour for set up and breakdown). Proprioception testing will take place before, during and after SCS stimulation.

Figure 3: TTDPM test using a Biodex

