The spinal cord relies on input from the motor cortex as well as sensory information from the extremities to carry out specific actions. For example, recent evidence suggests that preservation of temporally specific proprioceptive information via dorsal column primary afferent fibers is critical for motor behaviors such as ambulation. Since the spinal cord is exposed during the placement of the SCS device, information about a subject's motor and sensory spinal pathways can be easily obtained during the regular course of the procedure and compared to proprioceptive and motor responses once the subject is awake and moving with the device turned on. Our lab specializes in electrophysiological recordings in subjects undergoing spinal cord stimulator (SCS) implantation for CLBLP, while MUSC's Locomotion Laboratory specializes in quantifying proprioception and movement in human subjects. In this proposal, we will apply these techniques to subjects with CLBLP to determine effects of spinal neuromodulation on motor and sensory thresholds, proprioception, and kinematics. Our plan includes the following specific aims:

**Aim 1. Compare the effects of LFTS and HFBS on motor and sensory thresholds intraoperatively.** Question: Do HFBS waveform patterns modulate motor and sensory thresholds to allow more information to reach the spinal cord? In this aim, we will measure sensory and motor spinal thresholds in subjects undergoing SCS implantation during stimulation of epidural paddle contacts. *We hypothesize that HFBS will reduce motor and sensory thresholds relative to LFTS during epidural paddle activation.*

**Aim 2. Determine the effect of HFBS on proprioceptive afferent signaling from lower extremity muscle groups.** Question: Does HFBS, when compared to traditional LFTS, allow for increased spatial limb awareness during passive motion? In this aim, postoperative subjects from SA1 will undergo isokinetic passive proprioceptive testing before, during and after spinal cord stimulation with HFBS and LFTS parameters targeting musculature surrounding the knee. *We hypothesize that subjects will have increased awareness of the lower limb in space through passive movement during optimal HFBS compared to optimal LFTS parameters.*

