In 2009 Harkema et al investigated the motor effects from LFTS at intensities strong enough to elicit paresthesias, ranging from 5-60 Hz (frequency), 210 to 450  $\mu$ s (pulse width) and amplitude ranging from 0.1 to 8.0 V. Using these parameters, LFTS was found to elicit lower extremity muscle activity including co-activation during standing, rhythmic activation during stepping, and mechanically appropriate activation of agonist lower extremity muscles during weight shift in a subject with spinal cord injury. Additionally, Gill et al introduced the application of multiple independent current control (MICC) which allows for different stimulation parameters on the paddle to be delivered in tandem, innervating spatially distinct regions of the spinal cord. The MICC programs supported bilateral tasks, suggesting that complex charge delivery via MICC can enable independent modulation of both spinal sensory and motor neuron pools.

The ability to program customized HFBS patterns may help to address another important factor in potentially expanding the use of SCS to other indications, including movement: preservation of proprioception. The amount of compromised afferent information during traditional spinal cord stimulation via LFTS is dependent upon the quantity of dorsal column primary afferents recruited and is proportional to increases in current and pulse width. Traditional stimulation parameters (15Hz-100Hz, 210 $\mu$ s-450 $\mu$ s, 4.5mA-9.0mA) were found to cause decreased interneuron modulation of inhibitory/excitatory interneurons from antidromic collision when amplitudes are high enough to innervate their homonymous motor neuron pool to activation threshold. However, high frequency burst stimulation (HFBS) at 600Hz was found to illicit motor neuron activation with a 39.8% reduction in current amplitude and 15% recruitment of modeled homonymous afferents, as opposed to 45% recruitment utilizing LFTS to elicit similar motor neuron activation.

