### Step 3: Body weight support and treadmill (BWST) testing before, during and after SCS stimulation

Figure 4:  
Demonstration of treadmill walking while undergoing 3-D kinematic tracking and EMG capture.

All of the following are for research purposes and not considered standard of care for SCS surgery. The following methods for gait and EMG module analysis have been developed and extensively tested by MUSC researchers at the College of Health Professions. Similar to step 2, LFTS and HFBS patterns will be compared by systematically testing each individual contact on the paddle while investigating for changes in stepping speed, pattern and EMG modulating complexity. Regarding EMG module analysis, muscle activity will be recorded bilaterally via surface EMG from the medial gastrocnemius, soleus, tibialis anterior, rectus femoris, vastus medialis, biceps femoris, semimembranosus and gluteus medius. Furthermore, subjects will also have active LED markers placed over their clothes in order to track whole body kinematics throughout this portion of the study.

First, subjects will walk across a GAITRite mat (CIR Systems, Franklin, NJ) to measure self-selected overground walking speed and other spatiotemporal gait parameters. Subjects will then be permitted to practice walking on the Instrumental Treadmill until they feel comfortable. To optimize capture of steady state data on the treadmill, each subject will walk for approximately 10 sec prior to the 30 sec of data collection (40 sec per trial). This will allow capture of at least 10 consecutive steady state gait cycles (depending on cadence) per each amplitude selection for each stimulation delivery technique, which will be defined by parameters found during walking SCM. We will allow as much rest as needed between trials. For all trials, subjects will wear their own low-heeled shoes. A safety harness (Robertson Mountaineering, Fort Collins, CO) mounted to the laboratory ceiling will be worn by the participant to protect them in the event of loss of balance. Our research team anticipates data collection to last approximately 2 hours per subject for this step (1 hour for walking SCM and gait analysis and 1 hour for set up and breakdown). For their participation in step 2 and step 3 of the study, participants will be

Date: 8/1/19

Version: 01

remunerated \$50.00 in the form of a check (\$10.00 for lunch reimbursement and \$40.00 for completion of steps 2 and 3).

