#### **TTDPM**

While testing for proprioception retention of the lower extremities, subjects may encounter discomfort due to non-volitional muscle activation that hinders passive movement. To mitigate this risk, the Biodex system has a subject-controlled trigger that immediately stops the dynamometer's passive motion and may be activated at any time a subject experiences discomfort or pain during the test.

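### Aim 2 defines neither *optimal* nor a common intensity criterion and describes no EMG during TTDPM, so an HFBS–LFTS difference can mix proprioception with evoked contraction or unequal drive

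*Combined protocol and SAP*

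**What the plan says.** Section 1.0, Aim 2, directs both patterns at the muscles around the knee. It expects better limb awareness "during optimal HFBS compared to optimal LFTS parameters". The protocol does not say what makes a setting optimal.

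Section 9.0, Step 2, starts with stimulation configuration mapping (SCM), with surface EMG pads on the muscles of interest, "in order to determine electrode and parameter configurations that elicit activation of lower extremity musculature". Mapping is supine: "Subjects will comfortably lie supine on a large, low-rise rehabilitation mat". The proprioception test comes next and is seated: "The TTDPM protocol will begin with the subject sitting in the Biodex testing seat". Intensity appears there only under blinding: "The subject will be blinded as to the mode and intensity of stimulation: HFBS, LFTS, or no stimulation". The subject holds a switch that stops the dynamometer arm, to be pressed on perceiving movement or on feeling pain or discomfort. There are at least 10 trials per condition.

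Section 13.0, under TTDPM, warns that "subjects may encounter discomfort due to non-volitional muscle activation that hinders passive movement". The only mitigation given is the same switch.

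The Significance text in Section 2.0 reports that HFBS at 600 Hz achieved "motor neuron activation with a 39.8% reduction in current amplitude". Modelled afferent recruitment was 15%, against 45% with LFTS, for similar motor activation.

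**The concern.** TTDPM measures proprioception only if the limb is moved passively and the switch press means that movement was felt. Stimulation that contracts muscle at the tested joint threatens both conditions. It can resist or add to the movement, give the subject another cue, or cause discomfort that ends the trial with the same press as a detection.

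The contrast between patterns also depends on how strongly each is driven relative to its own motor threshold. If one pattern runs further above threshold than the other, a TTDPM difference may reflect that gap and not the waveform. Either mechanism could hide the hypothesised HFBS advantage or imitate it. The choice of setting could also differ among the 5 subjects, because no rule fixes it.

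**Working it through.** **1. Is there a stated figure to reproduce?** No. Section 5.0 gives 5 subjects without an effect size, standard deviation or power for TTDPM. The check is mainly a comparison of passages.

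**2. The passages side by side.**
- Target of stimulation: muscles around the knee (Section 1.0, Aim 2).
- Joint moved in the test: the knee (Step 2).
- Purpose of the preceding mapping: finding settings that activate leg muscle (Step 2).
- Evoked activity during TTDPM: foreseen, but handled only as a comfort risk (Section 13.0).
- Rule for setting HFBS and LFTS in TTDPM: none found.
- EMG: described for SCM and for walking, not for TTDPM. Section 10.0 lists EMG electrodes as a data source without tying them to TTDPM. For the Biodex it lists displacement data.
- Rule separating discomfort stops from detections: none found.
- Analysis: a two-way repeated-measures ANOVA with Tukey adjustment (Section 5.0), with no stated term for intensity or evoked activity.

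**3. What the planned data can identify.** Write the observed HFBS − LFTS difference as

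D = (effect of waveform on afferent signalling) + (effect of evoked contraction) + (effect of unequal drive).

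The no-stimulation condition and the before and after tests supply a baseline. Subtracting the same baseline from both patterns leaves all three terms in D. Without EMG in TTDPM and a record of each pattern's current relative to its motor threshold, the terms cannot be separated afterwards.

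**4. Does the matching rule matter? (Section 2.0 figures)**
- Let T be the LFTS current for a given motor activation. The HFBS current for similar activation is (1 − 0.398) × T = 0.602 × T.
- Matched on current: HFBS sits at 1/0.602 = 1.66 times the LFTS multiple of motor threshold.
- Matched on motor activation: modelled afferent recruitment is 45% against 15%, a ratio of 45/15 = 3.

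These are different comparisons. HFBS recruitment at equal current is not given, so nothing can be derived about the direction of the TTDPM difference under that matching.

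**5. Scale only, on assumed artefact sizes.** Take a two-sided 5% paired t-test with n = 5 (df = 4) and no true proprioceptive difference. Let an artefact shift D by b standard deviations of the within-subject difference, so the noncentrality is b√5. The false rejection rate is about 7%, 14%, 40%, 71% and 91% for b = 0.25, 0.5, 1.0, 1.5 and 2.0. The documents give no value of b, and this is not the planned ANOVA. It shows only that a moderate artefact would matter with 5 subjects.

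**The case against.** The strongest reply is that the plan compares the best setting of each pattern with the best setting of the other, which is a legitimate question that does not require equal drive. A map of what activates muscle can also be used to stay below contraction. Targeting knee muscles follows from the rationale in Section 2.0, which concerns afferent loss at amplitudes that bring the matching motor pool to threshold. The design is within-subject, with a no-stimulation condition, before and after tests and blinding to mode and intensity. The subject also reports the direction of movement, which may help to recognise some stops that were not detections. The study presents itself as comparable with proof-of-concept work.

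Much of this stands. It rules out insisting on a particular matching rule, and it means that targeting the knee is not a flaw in itself. It does not close the gap. A best-against-best comparison needs *optimal* defined. A plan to stay below contraction would have to be stated and checked in the test. Baselines and blinding leave the three components of D together. EMG that was never recorded cannot be recovered later, even in a pilot.

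A reader might also want the main analysis limited to trials free of evoked activity. That would condition on a response to stimulation that may differ by pattern, and so could create bias. It belongs in a sensitivity analysis.

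**Conclusion.** The point holds in this form: a TTDPM difference between HFBS and LFTS *can* mix proprioception with evoked contraction or unequal drive, and the data as described could not tell them apart. The size of the contamination is unknown. The 1.66 and the threefold recruitment ratio show that the matching rule matters, on the assumption that figures cited for 600 Hz HFBS, with modelled afferents, carry over to these patients and settings.

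Stronger readings are not supported:
- *Supine settings are carried into the seated test, where thresholds differ.* Step 2 gives the order of the tasks but never says which settings TTDPM uses. Nothing in the documents shows a supine-to-seated shift. Step 3 uses settings "which will be defined by parameters found during walking SCM", which shows remapping for gait only.
- *Contamination will occur.* The risk statement is conditional.
- *The sign of the Aim 2 contrast depends on the matching rule.* Section 2.0 gives recruitment only at similar motor activation, and it ties the growth of afferent loss with current and pulse width to LFTS.

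This is a cheap improvement to Aim 2, not a reason to doubt the study as a whole.

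**What to change.** In Section 9.0, Step 2:

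1. Keep the SCM surface EMG pads on and record EMG throughout TTDPM.
2. Fix in advance a criterion for stimulation-evoked knee-muscle activity before the switch press, and apply it blind to condition to mark trials. Record discomfort stops separately so that they are not scored as detections.
3. Keep all valid detection trials as the main Aim 2 contrast. Report the contrast without marked trials as a sensitivity analysis, and report the rate of marked trials by pattern.
4. Reconcile Aim 2, Step 2 and the TTDPM risk text by defining *optimal* and stating the one criterion the investigator uses to set both patterns for seated TTDPM. Record each pattern's current and its EMG motor threshold. No level is proposed here.

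The cost is a little more recording and scoring time per subject. The pads are already placed for SCM in the same step. The sensitivity analysis may be sparse: the guaranteed minimum is 5 × 10 = 50 trials per condition, and a subject whose trials under one pattern are all marked drops out of that paired contrast, leaving 4.

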## 1.0 Objectives/Specific Aims

Each year, an estimated 34,000 spinal cord stimulation (SCS) surgeries are performed worldwide for treatment of debilitating chronic low back and leg pain (CLBLP). Although the commercial application of SCS to treat CLBLP was approved by the FDA in 1989, only in the past decade have significant advancements in stimulator technology been introduced. For instance, traditional SCS devices achieved reduction in pain using a type of stimulation known as low-frequency tonic stimulation (LFTS, below 100 Hz), which was dependent on induction of paresthesias (i.e., a tingling sensation) over the areas of pain perception. However, we now know that LFTS compromises sensory information flowing back to the spinal cord, which can be important in other spinal cord functions such as proprioception and movement. In contrast, recent innovations in stimulator technology now provide the capability to apply stimulation frequencies up to 10,000 Hz along with complex waveform patterns – known as high frequency burst stimulation or HFBS – that can mitigate pain perception without the induction of paresthesias and the negative consequences on proprioception and movement. We propose to study the effects of these recently introduced features in SCS technology on motor and sensory spinal thresholds, proprioception and movement in subjects with CLBLP.

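### Proprioception test (TTDPM): LFTS may be recognisable despite the stated blinding, and nothing described separates willingness to press, or a discomfort press, from detection of movement

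*Combined protocol and SAP*

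**What the plan says.** Section 9.0, Step 2 makes the blinding claim for the TTDPM task: "The subject will be blinded as to the mode and intensity of stimulation: HFBS, LFTS, or no stimulation". A blindfold and masking noise keep the subject from seeing or hearing the dynamometer arm. The subject holds a switch that stops the arm, "which is to be activated once the subject perceives movement". The same switch is also to be pressed "if the subject begins to feel any pain or discomfort throughout the task". The subject reports the direction of movement, and ten or more trials are planned per condition.

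Before the task, each contact is tested with both LFTS and HFBS "in order to determine electrode and parameter configurations that elicit activation of lower extremity musculature".

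Section 1.0 describes how the two waveforms feel when used for pain. Relief from LFTS is something "which was dependent on induction of paresthesias (i.e., a tingling sensation) over the areas of pain perception", whereas HFBS patterns are ones "that can mitigate pain perception without the induction of paresthesias". The TTDPM paragraph of Section 13.0 warns that during the test "subjects may encounter discomfort due to non-volitional muscle activation that hinders passive movement", and does not limit this to one waveform.

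Aim 2 (Section 1.0) predicts better limb awareness under HFBS than under LFTS. Section 5.0 plans 5 subjects and a two-way repeated measures ANOVA with Tukey adjustment. For this task, Section 10.0 lists displacement data from the dynamometer. No passage describes no-movement trials, a variable delay before movement, a check on blinding, or a rule for wrong-direction or discomfort presses.

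**The concern.** The angle at which a subject stops the arm depends on two things: how well the movement is sensed, and how much evidence the subject wants before pressing. If stimulation can be felt, the second can change with the condition. A subject who is more ready to press gets a smaller angle, which looks like better proprioception. One who waits because the leg is tingling gets a larger angle, which looks worse. A press made for discomfort before movement is noticed would also register as a small angle unless it is flagged.

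Any such shift would follow the stimulation condition, which is the factor Aim 2 compares. With 5 subjects, a shift shared by most of them would not average out, and without no-movement trials it could not be diagnosed afterwards. The blinding statement could then be cited as protection that the described procedures may not give.

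**Working it through.** The documents give no TTDPM effect size, standard deviation or scoring formula, so there is no plan figure to reproduce. The check sets the passages side by side and then illustrates the mechanism under stated assumptions.

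**1. Can the conditions be told apart?**
- LFTS against no stimulation: Section 1.0 makes LFTS depend on felt tingling, and no limit below perception is stated for the task. The two are likely to be distinguishable.
- LFTS against HFBS: Section 1.0 says only that HFBS can relieve pain without paresthesia. Settings for this task come after mapping for muscle activation, and Section 13.0 expects muscle activation during the test, so HFBS may be felt. The two may still differ in quality of sensation, and nothing planned would show it.
- Masking: the blindfold and headphones act on sight and hearing only.

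**2. Does a shift in criterion move the endpoint when sensitivity is fixed?** Assume that evidence for one of two directions accumulates with drift v = 1 and noise s = 1, and that the subject presses when it reaches ±c. At constant arm speed, angle is proportional to time. The mean time is (c/v)·tanh(cv/s²).
- c = 2.0: 2.0 × tanh(2.0) = 2.0 × 0.964 = 1.928
- c = 1.6 (20% lower): 1.6 × tanh(1.6) = 1.6 × 0.922 = 1.475, and 1.475/1.928 = 0.765
- c = 2.4 (20% higher): 2.4 × tanh(2.4) = 2.4 × 0.984 = 2.361, and 2.361/1.928 = 1.22

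So the angle falls by about 23% or rises by about 22% with no change in proprioception. A discrete-time simulation of the same model gives:

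| Criterion | Mean angle | Wrong-direction presses | False presses on no-movement trials |
|---|---|---|---|
| Baseline | reference | 1.5% | 29% |
| 10% lower | 11% lower | 2.6% | 38% |
| 20% lower | 23% lower | 3.5% | 48% |
| 30% lower | 34% lower | 5.3% | 60% |
| 40% lower | 46% lower | 7.8% | 73% |

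The no-movement window equals the baseline mean detection time. The absolute rates depend on the assumed drift and noise. What matters is that no-movement trials respond strongly to the shift and direction errors hardly at all.

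**3. Does the direction report catch it?** Keeping only correct-direction trials leaves the reductions at 11%, 23%, 34% and 46%. As an alarm it is weak. With 10 trials, the chance of at least one wrong direction is 1 − (1 − 0.035)^10 = 30% at the 20% shift, against about 14% at baseline. Under a pure-guess model with two directions, half the guesses are right by chance. If 20% of presses are guesses, 0.9^10 = 35% of ten-trial blocks show no error; if 10% are, 0.95^10 = 60%.

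**4. Discomfort presses.** Assume that a share g of presses are for discomfort and fall on average halfway to the detection angle. The mean angle then falls by g/2: 5% for 1 press in 10, and 10% for 2 in 10.

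**5. How precise would a false-press rate be?** If 1 trial in 5 has no movement, then x/(10 + x) = 1/5, so x = 2.5, or 2 to 3 per 10 movement trials. For zero false presses in n trials, the two-sided exact 95% upper limit is 1 − 0.025^(1/n).
- One subject: 84% (n = 2), 71% (n = 3)
- Pooled over 5 subjects, treated as independent: 31% (n = 10), 22% (n = 15)

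A per-subject correction would mostly add noise. A pooled rate is still coarse, and is useful for description.

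**The case against.** Three stronger readings are tempting, and the documents do not support them.

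- **HFBS is not felt, so blinding fails for the main contrast.** Section 1.0 speaks of pain relief, not of sensation during TTDPM, and Sections 9.0 and 13.0 make felt HFBS plausible. Section 2.0 also links paresthesia from LFTS to intensity.
- **The task has no no-movement trials.** Step 2 gives no full trial schedule and cites published methods for the task. Such trials are not described, which is different from being excluded.
- **An HFBS advantage would be an artefact.** The direction of bias is unknown. If tingling prompts earlier presses under LFTS, the bias runs against the Aim 2 hypothesis.

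It can also be said that blinding may mean only that subjects are not told the mode, and that the direction report is a safeguard. The first is fair and is a reason to restate the claim, not abandon it. The second stands in part: the report is a real check, but it has no analysis rule and little power with about ten trials. None of this answers the shared switch, which needs no assumption about how HFBS feels.

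**Conclusion.** The point holds in a limited form. Blinding of LFTS against no stimulation is doubtful on the protocol's own description, and blinding of LFTS against HFBS is uncertain. The endpoint is a self-initiated press, and nothing described separates a shift in response criterion, or a discomfort press, from a change in proprioception. Either could enter the Aim 2 comparison, in either direction.

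The documents give no figure for the size. The illustration, about 23% in angle for a 20% lower criterion, rests on an assumed model with assumed drift and noise. It shows that the effect can be material, not that it will occur. The change is worth making before testing starts, because the information cannot be recovered later.

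**What to change.** In Section 9.0, Step 2:

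1. Add no-movement trials at random positions (for example 1 in 5) and a random delay before movement, in every condition.
2. Record the reason for each press. Do not count discomfort or wrong-direction presses as detections, and report how many there were by condition. The switch's stopping function is unchanged.
3. Report the false-press rate by condition, pooled over subjects, beside the TTDPM threshold. Keep any threshold corrected for false presses as a supporting analysis only. Correct-direction scoring does not remove a criterion shift, so the false-press rate is the main evidence on it.
4. Restate the blinding as subjects not being told the mode or intensity. After each block, ask which mode they think was on and whether they felt tingling, and report the answers with the Aim 2 result.

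The cost is 2 to 3 short trials per 10 in each condition and one question per block, so a slightly longer session around the hour planned for TTDPM. No stimulation setting or clinical care changes.
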